4.1. Handling of follow-up survey results

Survey will be conducted at initiation of run-in period (visit 1), immediately before initiation of randomized treatment (visit 2), and 8 & 52 weeks after initiation of treatment (visits 3 & 4). Visit 3 survey results within 2 weeks of the planned visit will be used for statistical analysis and visit 4 survey results within 4 weeks of the planned visit will be used for statistical analysis. When participants are complicated with concomitant disease which can affect eGFR, survey results after onset of the disease will be deleted as missing values.

4.2. Missing values

In principle, missing values will not be imputed.

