4.2 Expected number of participants and implementation period

Expected number of participants: 100 (50 in each of treatment groups A and B)

Research period: After approval by the Ethical Review Committee - February 28, 2021

Research registration period: After approval by the Ethical Review Committee - November 30, 2018

The basis for setting the number of expected participants.

We predicted that a sample size of 100 participants the study would provide 90% power to detect differences in the primary outcome (change in eGFR) of 15 mL/min/1.73m² per year between the randomized groups based on the findings of previous studies,^{14, 15} assuming a standard deviation of 20 mL/min/1.73m², a drop-out rate of 20%, a type I error rate of 5%, and the use of a two-sided significance test.

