In addition to the aforementioned, AST, ALT, serum creatinine, Na, K, Cl, serum uric acid, and urinalysis will be conducted on each outpatient clinic day from 8W to 52W to track the side effects of hepatic and renal disorders.

(9) Compliance with research treatment

After each treatment period, the subjects will be questioned about the study drugs' medication status in the following four stages.

(1) I almost took it (more than 90%)

(2) Sometimes forgot to take the medication (more than 70% to less than 90%)

(iii) More than half of them took it (more than 50% to less than 70%)

④ Less than half of the patients took the drug (less than 50%)

(10) Concomitant medications

No drug modifications will be made during the Run in phase and Treatment phase 1 if possible. The types and daily doses of antihypertensive drugs, diuretics, antidiabetic drugs, lipid drugs, and basic renal failure drugs until the conclusion of the study will be evaluated.

(11) Adverse events

Assess adverse events during study participation

(12) Data collection

Data collection will be performed by a clinical research coordinator affiliated with the implementing medical institution or the researcher's institution.

[figure not shown]
6. Overview of the research agent

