(7) Change in XO activity from immediately before initiation of randomized treatment (visit2) to 8 & 52 weeks after initiation of treatment (visits 3 & 4) [unit: % / 8 weeks, % / 52 weeks, pmol IXP / min / mL / 8 weeks and pmol IXP / min / mL / 52 weeks]

(8) Change in hs-CRP from immediately before initiation of randomized treatment (visit2) to 8 & 52 weeks after initiation of treatment (visits 3 & 4) [unit: % / 8 weeks, % / 52 weeks, mg / dL / 8 weeks and mg / dL / 52 weeks]

(9) Change in urinary 8-OHdG (8-hydroxy-2'-deoxyguanosine) from immediately before initiation of randomized treatment (visit2) to 8 & 52 weeks after initiation of treatment (visits 3 & 4) [unit: % / 8 weeks, % / 52 weeks, ng / mL / 8 weeks and ng / mL / 52 weeks]

(10) Change in urinary angiotensinogen from immediately before initiation of randomized treatment (visit2) to 8 & 52 weeks after initiation of treatment (visits 3 & 4) [unit: % / 8 weeks, % / 52 weeks, μ g / gCr / 8 weeks and μ g / gCr / 52 weeks]

(11) Change in urinary L-FABP from immediately before initiation of randomized treatment (visit2) to 8 & 52 weeks after initiation of treatment (visits 3 & 4) [unit: % / 8 weeks, % / 52 weeks, μ g / gCr / 8 weeks and μ g / gCr / 52 weeks]

2-7. Sample size estimation

Expected number of participants: 100 (50 in each of treatment groups A and B)

[Rationale for sample size estimation]

The main objective of this study was to exploratively investigate the effect of febuxostat administration and benz bromarone on renal function in patients with hyperuricemia complicated by chronic kidney disease. Based on the results of previous studies, we expected the difference between the two treatments to be eGFR/52W 15 ml/min/1.73m².^{1,2} Then, we calculated α 0.05, power 0.8, δ 15, σ 20, and dropout rate as 20%.

2-8. Follow-up duration

Participants will be followed up for 52 weeks (treatment period 1 for 8 weeks and treatment period 2 for 44 weeks).

2-9. Research period

Research period: from approval by the Ethical Review Committee to February 28, 2021

Registration period : from approval by the Ethical Review Committee to November 30, 2018

3. Analysis population

Full analysis set (FAS): In accordance with the intention to treat (ITT) principle, all patients except for those without information after randomization will be included in the analysis.

Per protocol set (PPS): Sensitivity analysis excluding participants with protocol violation might be conducted.

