5.4. Primary analysis

Change in eGFR from immediately before initiation of randomized treatment (visit2) to 52 weeks after initiation of treatment (visit 4):

(eGFR at visit 4 – eGFR at visit2) / eGFR at visit 2 [unit: % / 52 weeks] and

eGFR at visit 4 – eGFR at visit 2 [unit: ml / min / 1.73m² / 52 weeks]

will be estimated and compared between randomized groups using unpaired t-test or analysis of variance (ANOVA). Mean differences in eGFR change between randomized groups, 95% confidence intervals and p values will be estimated. If there is significant imbalance in important factors in baseline characteristics, analysis of covariance (ANCOVA) will be used as sensitivity analysis. If missing values in the primary outcome are observed among ≥5% of participants, multiple imputation will be conducted as sensitivity analysis. These results will be summarized in Table (Primary analysis).

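### The primary eGFR test is a completers' comparison, although the SAP's full analysis set follows intention to treat; analyses that keep patients without a week-52 value are only sensitivity or secondary.

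*Protocol*

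**What the plan says.** - **Population.** SAP section 3 defines the full analysis set (FAS) under the intention-to-treat principle: "all patients except for those without information after randomization will be included in the analysis". Protocol 7.2 also calls the analyses ITT. Its own FAS asks for at least one dose and an eGFR before and after the start of treatment in phase 1. Neither definition requires a week-52 value.
- **Primary outcome and test.** SAP 5.4 compares the change from Visit 2 to Visit 4, in absolute and percentage form, by unpaired t-test or ANOVA.
- **Window.** SAP 4.1: "visit 4 survey results within 4 weeks of the planned visit will be used for statistical analysis". The same section sets to missing any results obtained after the onset of a concomitant disease that can affect eGFR. SAP 4.3 allows outliers to be set to missing.
- **Missing values.** SAP 4.2: "In principle, missing values will not be imputed". SAP 5.4 adds an exception: "If missing values in the primary outcome are observed among ≥5% of participants, multiple imputation will be conducted as sensitivity analysis".
- **Repeated measures.** SAP 5.5.2 plans a GEE on the week-8 and week-52 changes, reporting an overall mean difference between arms.
- **Expected loss.** Protocol 4.2 and SAP 2-7 both assume 20% drop-out.
- **After discontinuation.** Protocol 4.7 asks that Visit 3 and Visit 4 observations still be recorded for discontinued patients, with wording that appears to mean where possible.

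**The concern.** The stated analysis population and the stated primary test do not fit together. The SAP says that everyone with any follow-up is analysed, but the outcome cannot be calculated without a week 48 to 56 eGFR, and the t-test has no way to use a patient who lacks one. The headline result would carry an ITT label while comparing completers.

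What is at stake is bias. Several of the exits in Protocol 4.7 (adverse events, cardiovascular complications, renal replacement therapy) could plausibly be related to kidney function, and so could the SAP 4.1 rule that deletes values after a relevant disease. If such losses fall unevenly on the two drugs, the arm that loses more of its declining patients looks better than it is.

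**Working it through.** **1. The plan's own sample size.** Inputs from Protocol 4.2: "90% power to detect differences in the primary outcome (change in eGFR) of 15 mL/min/1.73m² per year", SD 20, two-sided 5%, 20% drop-out, 100 patients.

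n per arm = 2(1.960 + 1.282)² × 20²/15² = 37.4, so 38 per arm. That is 76 evaluable, and 76/0.8 = 95. With the t distribution it is 39 per arm, 78 evaluable, and 78/0.8 = 97.5, so 98. The stated 100 reproduces.

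With 40 evaluable per arm, power = Φ(15/(20√(2/40)) − 1.96) = Φ(1.39) = 0.918 (0.912 by t). With all 50 per arm it would be 0.963 (0.960), an upper bound, because a patient with partial data gives less than full information. The loss is already in the sample size, so lost power is not the issue.

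(SAP 2-7 gives power as 0.8 for the same inputs, which needs only 70 to 74 patients. That is a separate mismatch to reconcile.)

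**2. Who is in the primary test.** Take a patient with eGFR at Visits 2 and 3 and none in weeks 48 to 56.
- SAP section 3 FAS: included.
- Protocol 7.2 FAS: included.
- SAP 5.4 primary test: no outcome value and no imputation, so excluded.
- SAP 5.4 multiple imputation: included, as sensitivity.
- SAP 5.5.2 GEE: included, as secondary, but the target is an average over weeks 8 and 52.

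**3. How many.** 20% of 100 is up to 20 patients. The 5% trigger for imputation is 5 patients, so the plan's own figure is four times the trigger.

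**4. Size of the bias, by formula.** Let d be the amount by which drop-outs' true 52-week change is worse than completers', the same in both arms, and let a and b be the drop-out proportions. Completers overstate an arm's mean by a × d or b × d, so the between-arm difference is off by d(a − b). The values of d, a and b are assumptions.

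| d (mL/min/1.73m²) | 20% v 20% | 25% v 15% | 30% v 10% |
|---|---|---|---|
| 1 | 0 | 0.1 | 0.2 |
| 2 | 0 | 0.2 | 0.4 |
| 5 | 0 | 0.5 | 1.0 |
| 10 | 0 | 1.0 | 2.0 |

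Equal rates do not protect if only one arm's drop-outs differ: at 20% the bias is then 0.2d, the same as the last column.

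**5. Size of the bias, by simulation.** Assumptions: 50 per arm, true difference 2.0, random slope SD 5, residual SD 3. The SD of the 52-week change is √(25 + 2 × 9) = 6.6, and the correlation between the week-8 and week-52 changes is about 0.45. The difference and SD are in line with the supplementary tables in the file; they are not the design inputs of 15 and 20. The odds ratio is for drop-out per 1 mL/min fall at week 8. The likelihood estimate uses Visits 2, 3 and 4; a dash means no figure is to hand.

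| Drop-out (benzbromarone v febuxostat) | Odds ratio | Completers | Likelihood |
|---|---|---|---|
| 20% v 20% | none | about 2.0 | about 2.0 |
| 20% v 20% | 1.4, both arms | 2.0 | – |
| 25% v 15% | 1.2, both arms | 1.77 | 1.98 |
| 25% v 15% | 1.4, both arms | 1.7 | – |
| 30% v 10% | 1.1, one arm | 1.65 | – |
| 30% v 10% | 1.2, one arm | 1.34 | 1.98 |
| 30% v 10% | 1.4, one arm | 1.0 | 2.0 |

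Standard errors, completers v likelihood: 1.47 v 1.43 with equal unrelated drop-out, and 1.54 v 1.58 in the last row. The model costs little or nothing in precision.

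**The case against.** The case for leaving the plan alone has several parts.

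- **The plan already uses these patients.** A reader might infer that they vanish from every analysis. They do not: multiple imputation is pre-specified and 20% loss would trigger it, and the GEE keeps those with a week-8 value. Imputation and a likelihood model fed the same variables rest on the same missing-at-random assumption. This stands, and it reduces the question to which analysis is primary. That still matters, because the primary test carries the conclusion and it is the one that contradicts the stated population. The GEE does not fill the gap, since it targets an overall difference.
- **Twenty patients is a ceiling for drop-out.** Stopping treatment is not leaving the study, and Protocol 4.7 seeks Visit 4 data after discontinuation. This stands. In the other direction, the deletion rules in SAP 4.1 and 4.3 can add missing values that are not drop-outs.
- **The bias may be nil.** A reader might infer that the completers' estimate is half the truth. That needs 30% v 10% drop-out driven strongly by eGFR in one arm only, and nothing in the documents supports either assumption. With equal, equally related drop-out there is no bias in the difference.
- **The simulation favours the model.** Drop-out was generated from the observed week-8 change, so the likelihood estimate is unbiased by construction. It shows what the model can remove, not that it removes everything.
- **Interim creatinine.** A reader might infer that the creatinine that "will be conducted on each outpatient clinic day from 8W to 52W to track the side effects" should enter the primary analysis. These are safety tests with no fixed schedule or windows, so they do not fit a model with visit as a category. They begin only at week 8, so those who leave earlier may have none.

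**Conclusion.** The point holds as a mismatch between the stated ITT population and a primary test limited to completers, with a risk of bias that the plan controls only outside its primary analysis. That reading rests on the text alone.

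The size of the bias rests on assumed drop-out rates and assumed links to eGFR. With a true difference of 2.0 mL/min/1.73m², the completers' estimate runs from 2.0 (no bias) through about 1.7 to 1.8 in a moderate case to about 1.0 in an extreme one. It arises only when drop-out is related to eGFR and differs between arms, in rate or in how it depends on eGFR. The documents do not show that this will happen, and they do not support a claim that power is lost. The change is worth making because the better primary analysis uses visits already scheduled and needs a weaker missing-data assumption than the completers' test.

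**What to change.** In SAP 5.4, make the primary estimate the week-52 between-arm contrast in change from Visit 2, taken from a likelihood-based repeated-measures model of eGFR at Visits 2, 3 and 4. Use visit as a category and treatment-by-visit terms, and include all FAS patients. For the percentage form of the endpoint, state the counterpart, for example the same model on the percentage changes at Visits 3 and 4. Keep the completers' t-test as a sensitivity analysis.

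Reword SAP 4.2 to say that missing eGFR is handled by this model. Bring the FAS definitions in SAP section 3 and Protocol 7.2 into line with each other and with the model. Report the number of patients contributing at each visit, by arm.

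The cost is wording and modest programming; no new data are needed. The downside is reliance on missing at random, which is weaker than the completers' assumption but still an assumption. For patients who die or start renal replacement therapy, the model implies a hypothetical week-52 eGFR, and the SAP should say so.

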4.3. Outlier

Outliers may be deleted as missing values based on consensus in medicine.

4.4. Transformation of continuous variables

A continuous variable, which does not follow a normal distribution, may be log-transformed.

5. Statistical analysis

5.1. Basic rule

The level of statistical significance will be 0.05 (two-sided). A continuous variable will be summarized as mean, SD, median, interquartile range, number of participants with missing values. A categorical variable will be summarized as number of cases, percentage, number of participants with missing values. Denominator of percentage will be number of participants with

available data.

5.2. Participant flow

Number of registered participants, randomized participants, analysis population, treatment discontinuation and drop-out will be summarized in Figure (Participant flow) .

Participants who did not receive randomized treatment, those who were excluded after registration, those who discontinued treatment or dropped out will be summarized by reason. Drop-out rate will be estimated as number of participants with discontinuation and drop-out / number of FAS. These results will be included in Figure (Participant flow) .

5.3. Baseline characteristics

Baseline characteristics, test results and concomitant treatment will be summarized by randomized groups in Table (characteristics, test results and concomitant medications) .

5.4. Primary analysis

Change in eGFR from immediately before initiation of randomized treatment (visit2) to 52 weeks after initiation of treatment (visit 4):

(eGFR at visit 4 – eGFR at visit2) / eGFR at visit 2 [unit: % / 52 weeks] and

eGFR at visit 4 – eGFR at visit 2 [unit: ml / min / 1.73m² / 52 weeks]

will be estimated and compared between randomized groups using unpaired t-test or analysis of variance (ANOVA). Mean differences in eGFR change between randomized groups, 95% confidence intervals and p values will be estimated. If there is significant imbalance in important factors in baseline characteristics, analysis of covariance (ANCOVA) will be used as sensitivity analysis. If missing values in the primary outcome are observed among ≥5% of participants, multiple imputation will be conducted as sensitivity analysis. These results will be summarized in Table (Primary analysis).

5.5. Secondary analysis

5.5.1. Secondary outcomes

Same analysis approach as the primary outcome will be applied to secondary outcomes. With regard to rate of attainment of serum uric acid level <6.0 mg/dl at 8 & 52 weeks after initiation of treatment, odds ratios, 95% confidence intervals and p values will be estimated using Fisher's exact test, chi-squared test and/or logistic regression models. If there is significant imbalance in important factors in baseline characteristics, multivariable logistic regression models will be used as sensitivity analysis. These results will be summarized in Table (Secondary analysis).

5.5.2. Repeated measure analysis of primary outcome

Change in eGFR from immediately before initiation of randomized treatment (visit2) to 8 & 52 weeks after initiation of treatment (visits 3 & 4) will be used as repeated measure and overall mean differences in eGFR change between randomized groups, 95% confidence intervals and p values will be estimated using Generalized Estimating Equations (GEE). Overall mean change in eGFR and 95% confidence interval in each randomized group will also be estimated. If there is significant imbalance in important factors in baseline characteristics, GEE including such factors as covariates will be used as sensitivity analysis. These results will be summarized in Table (Repeated measure analysis of primary outcome).

5.6. Medications

Study treatment and concomitant medications at 8 & 52 weeks will be summarized in Table (Medications).

5.7. Safety analysis

Serious adverse events during study treatment will be summarized by randomized groups in Table (Safety outcomes). Serious adverse events reported by physician will be used for the analysis. The difference in frequency of serious adverse events will be compared between randomized groups using chi-squared test and results will be summarized in Table (Safety outcomes).

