6.2 Anticipated adverse reactions

The following side effects have been reported.

Excerpt from Febuxostat Appendix (Revised November 2013 (5th Edition))

(1) Serious adverse reactions: Hepatic dysfunction (frequency unknown), Hypersensitivity (frequency unknown)

(2) Other side effects

Type \ Frequency	Frequency unknown Note)	Less than 1-5	Less than 1
blood	thrombocytopenia anemia		decreased white blood cell count
endocrine			Increased TSH
nervous system	Headache, taste disorder		Tingling sensation in limbs, floating dizziness, somnolence
heart	pulsation		ECG abnormality
gastrointestinal			Diarrhea, abdominal discomfort, nausea, abdominal pain
Liver and Biliary System		Abnormal liver function test values [increased ALT (GPT), AST (GOT), γ -GTP, etc.].	
skin	urticaria		Rash, pruritus, erythema
musculoskeletal system		arthralgia	Limb pain, limb discomfort, increased CK (CPK)
Renal and urinary tract	decreased urine output		Increased beta-N-acetyl D-glucosaminidase, increased urinary beta2-microglobulin, increased blood creatinine, increased blood urea, frequent urination
Other	swelling		Fatigue, dry mouth, increased triglycerides in the blood, increased CRP

Note 1) Not observed in domestic clinical trials, but observed in foreign countries.

Excerpt from Benzboromarone® Tablets 25 mg, 50 mg (Revised May 2013 (11th Edition))

(1) Serious adverse reactions: Hepatic dysfunction (frequency unknown): Severe hepatic disorders such as fulminant hepatitis and jaundice may occur.

(2) Other side effects

Frequency Type	0.1% or more	Less than 0.1	Frequency unknown
Hypersensitivity ^{Note 1)}	Itchiness, rash, urticaria	Facial redness, erythema	photosensitivity
Liver ^{Note 2)}	Increase in AST (GOT) and ALT (GPT) rise	Increase in Al-P	jaundice
digestive organs	Gastric discomfort, Gastrointestinal disorders, Diarrhea, Soft stools, Heartburn	Stomachache, abdominal pain, nausea, roughness in the mouth	
Other		Edema, cardiac discomfort, headache	

(Note 1) If any of these symptoms occur, the administration should be discontinued.

(Note 2) If such symptoms occur, the administration should be discontinued and appropriate measures should be taken.

7. Outcome variables

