7.2 Statistical analysis

(1) Target population for analysis

Case handling will be assessed by the principal investigator. The largest Full Analysis Set will be presented as the patient population enrolled in the study, who have received at least one study treatment, and whose eGFR has been evaluated before and after the treatment initiation in treatment phase 1.

(2) Statistical analysis

ITT analysis will conduct the analyses. The subject background will be evaluated by

calculating frequency summaries or summary statistics for each allocation group and conducting Student's t-test and Pearson's chi-square test.

The primary endpoint will undergo an unpaired t-test (or non-parametric test in the case of non-normal distribution). For the secondary endpoints, the corresponding t-test (or non-parametric test for non-normal distribution) will be conducted. The rate of attainment of serum uric acid levels of 6.0 mg/dL or less will be compared using Pearson's chi-square test.

For adverse events, the frequency, and prevalence of occurrence will be calculated for each event.

The significance level of the test is 5% two-sided unless otherwise stated. For estimating intervals, 95% confidence intervals are used.

8. What to do in the event of an adverse event

If a negative event is noticed, the treating doctor should act right away to address it and document the progress in the patient's medical file. Adverse events should be reported in the case report form.

Adverse events that fall under the following categories should be reported to the medical institution's leader following the medical institution's regulations as serious adverse events.

- (1) Deadly things
- (2) A threat to life.
- (3) Hospitalization for treatment or extension of hospitalization period
- (4) Permanent or significant disability or malfunction
- (5) Those with congenital anomalies.

9. Informed consent and provision of information to study participants

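### SAP 5.7 tabulates serious adverse events only, although protocol 7.2 commits to reporting every adverse event, so recorded non-serious events have no place in the planned safety results by arm

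*Protocol*

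**What the plan says.** Protocol 7.2 sets the adverse event analysis in one sentence: "For adverse events, the frequency, and prevalence of occurrence will be calculated for each event". It does not limit this to serious events and names no test between arms.

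Protocol section 8 covers collection: "Adverse events should be reported in the case report form". It then defines serious events as a subset by five criteria. Protocol 5.2 (11) is equally broad: "Assess adverse events during study participation".

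SAP 5.7 is narrower at each step. On tabulation it says "Serious adverse events during study treatment will be summarized by randomized groups in Table (Safety outcomes". On the source it says "Serious adverse events reported by physician will be used for the analysis". On inference it says "The difference in frequency of serious adverse events will be compared between randomized groups using chi-squared test". The SAP's list of figures and tables (section 7) has one safety table, Safety outcomes, and no other SAP section tabulates non-serious adverse events.

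**The concern.** The SAP says that its purpose is to define the analysis methods in detail, so an analyst will build the tables that it lists. Those tables contain no row for an event below the seriousness criteria.

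This matters because the trial sets one active drug against another, and relative tolerability is part of what readers will want from it. Protocol 6.2 lists many reactions for both drugs that would usually fall short of those criteria, including liver enzyme increases, skin reactions, gastrointestinal symptoms and, for febuxostat, arthralgia. Protocol 4.4 foresees gouty arthritis during follow-up. Protocol 5.2 (8) adds laboratory tests on clinic days between weeks 8 and 52 "to track the side effects of hepatic and renal disorders". A safety report limited to serious events would say little about any of these by arm, although adverse events are collected.

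**Working it through.** The documents state no safety figure, so there is none to reproduce. The main check sets the texts side by side. Two small calculations then bound what can be claimed.

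**1. Scope**
- Collected: adverse events of any severity, on the case report form (protocol section 8; protocol 5.2 (11)).
- Promised: a descriptive frequency for each event (protocol 7.2).
- Planned in the SAP: serious events only (SAP 5.7), in one table (SAP section 7).
- Left without a table: adverse events that are recorded but not serious.

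**2. What kind of event is left out**
- Protocol 6.2 names two serious reactions for febuxostat (hepatic dysfunction, hypersensitivity) and one for benzbromarone (hepatic dysfunction).
- Its tables of other reactions have ten organ-class rows for febuxostat and four for benzbromarone. Most of what the protocol anticipates therefore lies in the class that SAP 5.7 omits.
- The severe end is not lost. The benzbromarone warning "Severe hepatic disorders such as fulminant hepatitis and jaundice may occur" describes events that would ordinarily meet a seriousness criterion and be counted.

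**3. How many events that might be**
- The documents give no expected rate for this trial. The febuxostat table puts abnormal liver function tests and arthralgia in a column headed by the range 1 to 5.
- If that means 1% to under 5% of patients (an assumption, since the unit did not survive), then with 50 per arm (protocol 4.2) the expected number per event is between 50 × 0.01 = 0.5 and 50 × 0.05 = 2.5 patients in that arm.
- For benzbromarone the top category is 0.1% or more, with no upper limit, so no comparable range can be given.
- Counts for any single event may well be small. The value of the table is descriptive.

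**4. Whether the chi-squared test is a separate problem**
- Take assumed serious event rates of 4% and 10% with 50 per arm, that is 2 and 5 patients. The smallest expected cell is (2 + 5)/2 = 3.5, below the customary 5.
- Pearson statistic: (5 − 2)² / (2 × 50 × 0.07 × 0.93) = 9/6.51 = 1.38, p about 0.24. Fisher's exact test gives about 0.44. The conclusion is the same.
- The true two-sided size at nominal 0.05 was found by adding the binomial probabilities of all pairs of counts that the test rejects, under equal rates in both arms. With 50 per arm and rates of 1%, 2%, 5% and 10%, chi-squared has size 0.002, 0.013, 0.043 and 0.051. Over rates of 1% to 15% and 40 or 50 per arm, it peaks at about 0.059. Fisher's test stays at or below 0.026.
- Small expected cells are likely here (probability 0.97 at a 5% rate and 0.45 at 10%, with 50 per arm), but they do not make the test materially misleading.

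**5. What other sections already cover**
- Renal function: eGFR is computed from serum creatinine and compared between arms at weeks 8 and 52 (SAP 2-6, 5.4, 5.5).
- Discontinuations: SAP 5.2 summarises them by reason, and adverse events are one reason (protocol 4.7). SAP 5.2 does not say that this will be shown by arm.
- Neither replaces a table of non-serious events by term and arm.

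**The case against.** The strongest reply is that SAP 5.7 is silent on non-serious events rather than excluding them, so the commitment in protocol 7.2 still stands and could be met at reporting. It is also true that protocol 7.2 promises description only. The test in SAP 5.7 is an addition, and no promised comparison has been removed. Both points stand. They make this a gap in scope and not a conflict of method. They do not close it, because the SAP is the working document for the analysis and its table list has no place for these events.

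A reader might also infer more than the documents support:

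- **That chi-squared is unreliable here.** The size calculation does not bear this out, and Fisher's test is only more conservative. SAP 5.5.1 allows Fisher's test for uric acid attainment and 5.7 does not, but that is a matter of consistency.
- **That reliance on physician reports is a defect.** It agrees with protocol section 8, where the treating doctor documents events.
- **That no renal safety data are analysed.** Creatinine enters through eGFR at weeks 8 and 52. Only the clinic-day values in between are not used.
- **That every laboratory value is ready to tabulate.** The extra clinic-day tests in protocol 5.2 (8) are not in the schedule in protocol 5.1 whose results go into the case report. AST and ALT at the scheduled visits are.

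**Conclusion.** The point holds as a mismatch of scope: the protocol commits to all adverse events, and the SAP provides for serious ones only. It affects the completeness of the safety report and does not touch the primary eGFR comparison. It should be corrected, but it does not threaten the trial's validity.

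Its size in events cannot be given, because the documents state no adverse event rates for this trial. The range of 0.5 to 2.5 patients per event applies to febuxostat only and rests on reading the column heading as a percentage. The conclusion assumes that the SAP's table list will be followed as written, and that a liver enzyme rise or gouty arthritis counts as an adverse event only where the physician records it as one. Hepatic or gout events that meet a seriousness criterion are already covered.

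**What to change.** Amend SAP 5.7 and the Safety outcomes table to show all recorded adverse events, serious and non-serious, by event term and randomized group in the safety analysis set. Give counts and percentages and, optionally, risk differences with 95% confidence intervals. No test on non-serious events is needed to meet protocol 7.2. Keep the existing serious-event summary and comparison.

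Where AST and ALT values are captured, summarise hepatic enzyme elevations by arm in the same table and state which visits contribute. Values from the additional clinic days should be included only if they are confirmed to be in the database.

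The cost is a change of SAP wording and one more table. Adverse events already go on the case report form, so no new data collection is needed.
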